**The Effect of The Mobile Application on Treatment Adherence, Self-Management, and
Quality of Life in Patients with Acute Myocardial Infarction Undergoing Primary
Percutaneous Coronary Intervention**

[name], [name],

[name], Msc, RN, Research Assistant (Corresponding author)

Department of Nursing, Trakya University Faculty of Health Sciences, Edirne, TURKIYE

Orcid No: [name]

e-posta: [contact]

[name] [name], Msc, RN, Associate Professor

Department of Nursing, Trakya University Faculty of Health Sciences, Edirne, TURKIYE

Orcid No: [name]

e-mail: [contact]

Address for Correspondence:

[name], Msc, RN, Research Assistant

Address: [name]

[contact]

[contact]

e-mail: [contact]

Background and Aim: Acute myocardial infarction is a clinical condition with high mortality and morbidity rates. Ensuring patient adherence to treatments and lifestyle recommendations after discharge is crucial for effective post-acute myocardial infarction management. This study aimed to determine the impact of the mobile application on treatment adherence, self-management, and quality of life in patients with acute myocardial infarction undergoing primary percutaneous coronary intervention.

Study's Methods

Study design and sample

The study was conducted as a prospective (6-month follow-up), two-group (control and intervention), randomized controlled, experimental study.

The universe of the study consisted of patients who had their first time ST segment elevation MI (STEMI) undergoing PPCI in the Cardiology Clinic of a university hospital in Edirne, Turkey, between 01.11.2021 and 10.07.2024. In determining the sample of the study, power analysis was performed with reference to the study of Turan Kavradım and Özer (68). The effect size of the study was found to be 0.92 and considering this effect size, it was determined that it was sufficient to include a total of 54 patients, 27 in each group, at 95% power and 0.05 significance level. However, considering a 20% loss rate during the study period (30), it was aimed to reach a total of 66 patients, 33 patients for each group. Patients who volunteered to participate in the study were determined in accordance with the inclusion criteria. The selection of patients to the intervention and control groups was made using the simple randomization method. According to the randomization list, the groups were matched based on the time of discharge from the clinic of the patients. For patients who were discharged on the same day, the matching was based on their hospitalization times. The inclusion criteria were as follows: the patients who (1) had first time STEMI undergoing PPCI, (2) are over 18 years of age, (3) have a smartphone, (4) have internet access, (5) have orientation to place, time and situation, (6) have no problems with vision, hearing and speech, (7) are at least literate, (8) regularly come in for the doctor's check up, and (9) volunteer to participate in the study. Among the volunteers participating in the study, those who wanted to leave the study (2 patients) and those who didn't come in for the doctor's check up (3 patients) were excluded from the follow-up. Therefore, the study was completed with 61 patients, 30 in the intervention group and 31 in

the control group. The study design and implementation were based on the principles in the CONSORT (Consolidated Standards of Reporting Trials) list (Figure 1).

[figure not shown]

Figure 1. Flow chart of design and recruitment of participants according to CONSORT statement

Study Protocol

Education booklet

In the study, firstly, an education booklet was created by the researchers to be used as an education material to provide self-management in patients with AMI. During the development phase of the education booklet, expert opinions were obtained from a total of 9 people, including 3 cardiologists, 4 academic nurses and 2 cardiology nurses. In line with the expert opinions, the necessary arrangements were made and an 18-page “Education Booklet for Patients Having Heart Attack” was created.

Mobile application and web page control panel

After the creation of the education booklet, the development process of the mobile application began. In the first stage, the content of the application was determined based on the education booklet and sample mobile application studies in the literature (30,66,71,73,74). In order to evaluate the content of the mobile application, expert opinions were obtained from 3 cardiologists, 4 academic nurses and 2 cardiology nurses.

In the second stage, a software company was contacted and the interface and logo of the mobile application called “MEDIFOLL” was designed. The interface of the application includes “Medication Information”, “Blood P. & Pulse”, “Notifications”, “Lifestyle” and “Contact” sections. In the “Medication Information” section, medication entries are made. When it is time to take each medication, the mobile application sends a medication reminder notification to the user. “Blood P. & Pulse” section includes the screen where blood pressure and pulse are entered. The “Notifications” section displays personalized reminders sent by the researcher to the users via the web page control panel. Personalized reminders are information provided by the researcher to patients regarding the things to be considered in the post-discharge process, which are included in the education booklet. The “Lifestyle” section has been created for situations where the education booklet is lost or cannot be accessed in their environment where they are located. This section contains the information contained in the booklet under the heading lifestyle changes. The “Contact” section allows users to communicate with the researcher. In this way, patients can send their questions to the researcher via message.

In the third stage, a web page control panel was created that allows the mobile application to be controlled remotely, patient information to be viewed, data to be monitored, lifestyle information to be uploaded and viewed in the mobile application, personalized reminders to be sent to patients, and to be communicated with patients (<https://www.medicoll.com/>, <https://www.medicoll.com/brave/login>).

In the fourth phase, the application was purchased from Google Play Store and App Store. In the fifth stage, the mobile application and website were tested by experts for 1 week to determine usability of them and errors. Finally, a pilot study was conducted with 4 patients and the patients were allowed to use the application for a month. Patients who participated in the pilot study were not included in the study.

After the pilot study was completed, the Patient Information Form was filled out with all patients in the patient room before discharge. The researcher provided training to the patients in both groups in line with the education booklet and it was delivered to the patients. MEDIFOLL application was downloaded to the mobile phones of the patients in the intervention group and user registration was made. Information was provided to them on how to use the application and how to enter data such as blood pressure and pulse rate. The times of the use of medications prescribed during discharge were planned together with the patients and they were provided with the opportunity to enter their medications into the application.

Patients in the intervention and control groups were interviewed in the outpatient clinic 1 month, 3 months and 6 months after discharge, and the Patient Information Form, IUBÖ ve MIDAS scales were filled out. The flow chart of the research is presented in Figure 2.

Determination of the content of “Educational Booklet for Patients Who Have Had a Heart

Obtaining expert opinion for the educational booklet and developing the booklet

[figure not shown]

Figure 2. The flow chart of the research

Data collection tool

Patient Information Form: It, developed by the researcher through a literature review (15,18,30,36,59,67), consists of questions about the socio-demographic, the lifestyle, and the disease characteristics of the participants.

Medical Adherence Report Scale (MARS): The scale was developed by Horne and Hankins to determine medication adherence in individuals with chronic diseases. The Turkish validity and reliability of the scale was performed by Şen et al. (21). The scale has 5 items, one sub-dimension and 5-point Likert type. The total score obtained from the scale varies between 5 and 25. A high total score indicates adherence to medication treatment, while a low score indicates non-adherence to medication treatment. The Cronbach alpha value of the scale was found to be 0.78 in the study of Şen et al. (21) and 0.68 in this study.

Myocardial Infarction Dimensional Assessment Scale (MIDAS): The Turkish validity and reliability of the scale, developed by Thompson et al., was performed by Yılmaz et al. (71). The scale is used to determine the HRQoL of individuals with MI and consists of 35 items and 7 sub-dimensions (physical activity, insecurity, emotional reaction, dependency, diet, concerns over medication, and medication side effects). This 5-point Likert-type scale is scored between 0-4. Scores that can be obtained from the scale and its sub-dimensions vary between 0-100. The score is calculated with the formula: (Total score obtained from the sub-dimension/highest score that can be obtained from the sub-dimension) x100. As the scores obtained from the scale increase, the perceived HRQoL worsens. In the study of Yılmaz et al. (71), the Cronbach alpha value of the sub-dimensions of the scale was found to be between 0.79-0.90. In this study, it was found to be 0.93.

Ethical Consideration

The study was conducted in accordance with the Declaration of Helsinki. The study protocol was approved by the Scientific Research Ethics Committee of XXX University Faculty of Medicine (xxx), and written permission was obtained from the institution where the study was to be conducted (xxx). Necessary written consents were obtained from the patients.

Data Analysis

The data were evaluated using the IBM SPSS 22.0 (Statistical Package for Social Sciences 22.0) package program. The data to a normal distribution was examined by the Kolmogorov–Smirnov test. The number and percentage distribution were used to evaluate categorical data, and meanstandard deviation was used to evaluate continuous data. In the analysis of the data, Mann Whitney U test was used to compare the mean scores that did not show normal distribution between the groups and Student's t test was used to compare the mean scores that showed normal distribution. Pearson chi-square test and Fisher-Freeman-Halton Exact test analysis

were used to determine the relationship between groups for nominal variables. The statistical significance limit value was accepted as $p<0.05$.

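### The stated 95% power at 27 per group holds only for a one-sided test (two-sided power is 91%), and 33 per group falls just short of 27 after a 20% loss

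*Combined protocol and SAP*

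**What the plan says.** All the planning figures are in the section on study design and sample:

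- Effect size, taken from a cited earlier study: "The effect size of the study was found to be 0.92".
- Size and power: "sufficient to include a total of 54 patients, 27 in each group, at 95% power and 0.05 significance level".
- Loss: "considering a 20% loss rate during the study period", after which "it was aimed to reach a total of 66 patients, 33 patients for each group".
- Outcome: 61 patients completed, 30 in the intervention group and 31 in the control group.

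The paragraph does not say whether the calculation was one-sided or two-sided, which test it assumed, or which outcome and visit the 0.92 belongs to.

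The Data Analysis section uses Student's t test for normally distributed scores ("Student's t test was used to compare the mean scores that showed normal distribution") and the Mann-Whitney U test for the others. On significance it says only "The statistical significance limit value was accepted as" p<0.05. The aim has no direction either: "This study aimed to determine the impact of the mobile application on treatment adherence, self-management, and quality of life".

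**The concern.** A test at p<0.05 with no direction given, serving an aim with no direction given, is ordinarily read as two-sided. On that reading 27 per group is too few for 95% power at an effect size of 0.92, and the paragraph claims more power than the described analysis has.

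If a one-sided 0.05 test was intended, the power figure is right. But the chance of a false positive in favour of the application is then 5%, not the 2.5% of a two-sided 0.05 test, and the reader is not told. Sidedness affects how every p value in the report is read, so it should be explicit.

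The loss allowance is a separate and smaller matter. The target of 66 is presented as protecting the 54 evaluable patients against 20% loss, and it falls slightly short of doing so.

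**Working it through.** **Inputs.** Effect size d = 0.92, alpha 0.05, power 95%, 27 evaluable per group, 20% loss and a target of 33 per group, with 30 and 31 completers (all from the study design and sample section). The tests come from the Data Analysis section. Two assumptions are mine: 0.92 is a standardised mean difference (Cohen's d), and the power analysis used an independent two-sample t test with equal groups.

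**Formula.** With n per group, the test statistic follows a noncentral t distribution with 2n − 2 degrees of freedom and noncentrality d × √(n/2). Power is the probability that it exceeds the critical value. At n = 27 there are 52 degrees of freedom and the noncentrality is 0.92 × √13.5 = 3.380.

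**Step 1: reproduce the plan's figure.** One-sided at 0.05, the critical value is 1.675. The required n is 26.28, rounded up to 27, and power at 27 is 95.5%. This matches the plan exactly.

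**Step 2: the same calculation two-sided.** The critical value is 2.007. The required n is 31.70, rounded up to 32 per group (64 in total).

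| Evaluable per group | Two-sided power, d = 0.92 |
|---|---|
| 26 (about 33 less 20%) | 90.2% |
| 27 (planned) | 91.3% |
| 30 and 31 (completers) | 94.2% |
| 32 | 95.2% |
| 33 | 95.7% |

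Type II error at 27 is 100 − 91.3 = 8.7%, against the stated 5%.

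**Step 3: could rounding or approximation explain the gap?**

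- An effect size anywhere from 0.915 to 0.925 gives two-sided power of 91.0% to 91.5% at 27.
- The normal approximation gives 92.2% at 27 and requires 31 per group.
- Two-sided power of 95% at 27 per group needs d of about 1.00.

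None of these recovers 95% at d = 0.92.

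**Step 4: Mann-Whitney.** Its asymptotic relative efficiency under normality is 3/π = 0.955. The effective n is 27 × 0.955 = 25.8, with two-sided power of about 90%. For 95% power the requirement is 31.70 / 0.955 = 33.2, or 34 per group. Under this assumption the rank test widens the gap slightly.

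**Step 5: the loss allowance.**

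- Multiplying: 27 × 1.2 = 32.4, rounded up to 33. This matches the plan.
- Dividing, which is what retaining 27 requires: 27 / (1 − 0.20) = 33.75, rounded up to 34 per group (68 in total).
- Check: 33 × 0.8 = 26.4, below 27; 34 × 0.8 = 27.2.
- Loss that 33 per group covers: 1 − 27/33 = 18.2%.

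For reference, a design with 95% two-sided power after 20% loss would have needed 32 / 0.8 = 40 per group (80 in total).

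**The case against.** The strongest reply is that nothing in the plan is contradicted. It never says two-sided, its 27 can be reproduced, and the fault is an omission. That is fair as a description: if a one-sided analysis had been declared, the power figure would stand. But none was declared, and the aim and the significance limit are both worded without direction. Under the ordinary reading the 95% is not delivered. Under the other reading an unusual choice is undisclosed. The paragraph needs correcting either way.

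A second reply is that the effect-size type and the test are assumed here. That stands, and is why they are listed as assumptions. The exact one-sided match at 27 makes them likely but does not prove them.

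A third concerns weight, and most of it stands. The loss error is one patient per group, and at 26 per group one-sided power is still 94.8%. The shortfall below 27 arises only if the full 20% is lost. Actual loss was 5 of 66 (7.6%), and both groups finished above 27. Two-sided power at the completers' numbers is 0.8 points below the stated 95%, with a type II error of about 5.8%. The near-doubling of type II error belongs to the planned size, not to the numbers achieved.

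Finally, a corrected power figure is of little use unless it is tied to an outcome and a visit. That is right, and the fix asks for it.

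**Conclusion.** The concern holds. On the two-sided reading, power at 27 per group is 91.3%, which is 3.7 points below the figure stated, and 32 per group would be needed for 95%. The 27 is reproduced by a one-sided 0.05 t test that the documents never declare. The loss allowance is also miscalculated, by one patient per group (33 instead of 34).

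The first point is the material one; the second is minor. Neither means the completed trial is badly underpowered under its own assumption, since 30 and 31 completers give 94.2% two-sided power at d = 0.92. The correction should be made because the stated power is wrong for the analysis as ordinarily read, and because sidedness must be known to interpret the p values. All of this rests on 0.92 being Cohen's d for an independent two-group comparison of means.

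**What to change.** In the sample-size paragraph:

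1. State that the tests are two-sided, and repeat this beside the significance limit in the Data Analysis section. If one-sided testing was in fact intended, say so in both places, with the reason, and state that the 5% error lies wholly in one direction.
2. Name the type of effect size, the test assumed, and the outcome and visit to which 0.92 refers.
3. Replace the power claim with, for example: *With an effect size of 0.92 and two-sided alpha of 0.05, 27 patients per group give 91% power; 32 per group would be needed for 95%.*
4. Correct the loss sentence. Since 33 per group was the target actually used, the simplest wording is that it allows for 18% loss. Otherwise note that a 20% allowance requires 34 per group (68 in total).
5. Add that the 61 completers give 94% two-sided power at an effect size of 0.92.

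Any such restatement should be shown as a correction to the original planning figures. The cost is wording only: no patient is added and no analysis changes if two-sided p values are already used. The stated power becomes slightly less favourable.

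### Five enrolled patients, three of them for missing check-ups, were excluded from follow-up, and the readable text gives no analysis set or missing-score rule to bring them back into the comparison.

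*Combined protocol and SAP*

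**What the plan says.** All references are to the combined protocol and SAP.

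- **Design.** Study design and sample describes a "two-group (control and intervention), randomized controlled, experimental study".
- **Target and allowance.** The same section plans "considering a 20% loss rate during the study period", and "it was aimed to reach a total of 66 patients, 33 patients for each group".
- **Losses.** It then reports two patients who chose to leave and three who missed the doctor's visit: "check up (3 patients) were excluded from the follow-up. Therefore, the study was completed with 61 patients, 30 in the intervention group". The control group has 31. The readable text does not give the arm of each lost patient.
- **Criterion 8.** Regular attendance at check-ups is one of the nine inclusion criteria.
- **Timing of data.** Under Mobile application and web page control panel, "the Patient Information Form was filled out with all patients in the patient room before discharge", and the app set-up is described at the same point. Patients "were interviewed in the outpatient clinic 1 month, 3 months and 6 months after discharge", when the form, a scale labelled IUBÖ "ve MIDAS scales were filled out". The readable text does not define IUBÖ; I take it to be MARS.
- **Analysis.** Data Analysis lists software, a normality test, descriptive statistics, Student's t or Mann-Whitney U tests between groups, and chi-square or exact tests. It names no analysis set and no rule for missing scores.
- **Not visible.** Figure 1, captioned "Flow chart of design and recruitment of participants according to CONSORT statement", and Figure 2, the research flow chart, are not shown.

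**The concern.** Randomisation makes the two groups comparable as allocated. That protection weakens if patients leave the comparison because of something they do afterwards. Three of the five losses are defined by not attending, and MARS measures medication adherence, so attendance and outcome are plausibly related. Criterion 8 adds to the problem: a patient enrolled before discharge with a first STEMI has no post-discharge attendance to assess, so the criterion can operate only as a reason for removal after enrolment.

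The completers compared may therefore differ from the groups randomised. The app's benefit could be overstated if the lost intervention patients were the poorer adherers, or understated if the lost control patients were. In the readable text no scale is described before discharge, so no baseline score is available to adjust for this, unless Figure 2 shows one.

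**Working it through.** **Inputs from Study design and sample:** 2 withdrawals, 3 missed check-ups, completers 30 and 31, target 33 per group, planned loss 20%, planning effect 0.92 SD.

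**Assumptions of mine:** 33 were allocated to each arm (the text gives 33 only as a target), so 3 were lost from intervention and 2 from control; lost patients would score k = 1 or 2 SD worse than completers in their own arm; scores are compared by t test.

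**1. The plan's own counts.** 27 × 1.20 = 32.4, rounded up to 33 per group, or 66. Then 66 − 2 − 3 = 61 = 30 + 31. The counts agree. Loss is 5/66 = 7.6%, of which missed check-ups are 3/66 = 4.5%.

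**2. Bias of the completer comparison.** Overstatement of benefit = k × 3/33 if intervention losses are worse, minus k × 2/33 if control losses are worse.

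| Who is worse | k = 1 | k = 2 |
|---|---|---|
| Intervention losses only | +0.09 | +0.18 |
| Both arms' losses | +0.03 | +0.06 |
| Control losses only | −0.06 | −0.12 |

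If the 33/33 split is dropped, the extremes are all five from intervention (5/35: +0.14, +0.29) and all five from control (5/36: −0.14, −0.28).

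**3. Completer difference that gives p = 0.05.** The standard error in SD units is √(1/30 + 1/31) = 0.256. Two-sided, 2.001 × 0.256 = 0.51 SD. One-sided, 1.671 × 0.256 = 0.43 SD. Both are shown because sidedness is not stated. The planned 27 per group reproduces only with a one-sided t test (26.3, rounded up to 27); a two-sided test needs 32.

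**4. Difference needed once the lost patients are imputed and shifted.** Variance = 1/30 + 1/31 + k²p(1 − p)/N for each shifted arm, where p is the fraction lost and N = 33. Difference needed = bias + t × SE, with 59 degrees of freedom.

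Example, intervention losses only, k = 2: SE = √(0.0656 + 4 × 0.0909 × 0.9091/33) = 0.275, so 0.182 + 2.001 × 0.275 = 0.73 SD.

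| Who is worse | Two-sided, k = 1 / 2 | One-sided, k = 1 / 2 |
|---|---|---|
| Intervention losses only | 0.61 / 0.73 | 0.53 / 0.64 |
| Both arms' losses | 0.56 / 0.64 | 0.47 / 0.54 |
| Control losses only | 0.46 / 0.42 | 0.37 / 0.33 |

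At 33/33, the five patients can decide significance only if the completer difference lies between about 0.42 and 0.73 SD two-sided, or 0.33 and 0.64 SD one-sided.

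**5. At the planning effect of 0.92 SD (two-sided).** With intervention losses only, p = 0.002 at 1 SD and 0.009 at 2 SD; significance is lost only at a deficit of about 3.4 SD. If all five were intervention patients 2 SD worse, p = 0.03.

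**The case against.** The case on the other side is substantial.

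- **Completer-only analysis is an inference.** A reader might infer that the five patients' data were deleted. The text excludes them from follow-up, not from analysis, and does not say that earlier scores were discarded. A patient who stops attending cannot give later clinic scores, so part of this is ordinary missing data. This stands. What remains is that no step in Data Analysis brings these patients back.
- **The figures may fill the gap.** Figure 1 may show who was analysed and losses by arm; Figure 2 may show scale scores before discharge. This stands, and the point is limited to the readable text.
- **Loss is small.** It is 7.6% against 20% allowed for, and 30 and 31 completers exceed the 27 required. This answers a worry about power. An allowance in the sample size is not a rule for analysing the patients lost.
- **Criterion 8 may be the basis for removal.** It probably is, but an eligibility rule that depends on behaviour after enrolment does not justify removing a randomised patient.
- **A compulsory mixed model with many sensitivity estimates would be out of proportion.** Agreed; the fix below is smaller.

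**Conclusion.** The point holds, at minor to moderate severity. The readable text excludes enrolled patients from follow-up for non-attendance, describes only the completers, and states neither an analysis set nor a rule for missing scores.

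At 33/33 with deficits of 1 to 2 SD, the bias is about −0.12 to +0.18 SD. It matters for significance only if the observed completer difference is moderate, within the ranges shown above, and it would not overturn a difference of 0.92 SD. The deficits, the 33/33 split and the t test are assumptions. Only shifts towards worse scores were examined.

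Two stronger readings are not supported. One is that the app caused the difference in attendance: the readable text does not give losses by arm, and 3 against 2 under the assumed split would show nothing. The other is that the trial's conclusion is unsafe: the direction of any bias is unknown and its likely size is small.

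**What to change.** 1. State that all randomised patients are analysed in their assigned group using every MARS and MIDAS score collected at 1, 3 and 6 months.
2. State that missing a check-up is not a reason to remove a randomised patient, and that neither a missed check-up nor withdrawal from the study leads to earlier scores being dropped. Reconcile criterion 8 with this, since as worded it depends on attendance after enrolment.
3. Add one simple sensitivity analysis at 6 months for the MARS and MIDAS total scores. Impute the lost patients' scores in their assigned arm, then shift them worse by a stated amount (lower MARS, higher MIDAS) in one arm, then the other, then both. The interval should reflect the imputation. Label it post hoc, because the study is described as completed.

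A likelihood-based mixed model is one way to use all visits, but is not required. On the readable text, a patient who missed every visit would add nothing to such a model, which is why step 3 is needed.

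The cost is slightly more analysis work: with one stated shift, 2 scales × 3 placements = 6 estimates and no new data collection. The estimate may be slightly smaller or less precise.

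### No outcome scale is described before the intervention starts, so chance differences in starting quality of life cannot be shown or adjusted for; the comparison stays valid but may be less precise than it could be.

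*Combined protocol and SAP*

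**What the plan says.** Mobile application and web page control panel describes one contact before discharge, at which "the Patient Information Form was filled out with all patients in the patient room before discharge". Data collection tool says that this form "consists of questions about the socio-demographic, the lifestyle, and the disease characteristics of the participants"; it does not mention the outcome scales. The account then moves to booklet training for both groups and to the start of the intervention: "MEDIFOLL application was downloaded to the mobile phones of the patients in the intervention group and user registration was made".

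The scales enter at follow-up. Both groups "were interviewed in the outpatient clinic 1 month, 3 months and 6 months after discharge", and there "the Patient Information Form, IUBÖ ve MIDAS scales were filled out". The form is thus named on both occasions and the scales only on the later ones. 'IUBÖ' is not defined. MARS and MIDAS are the only two scales described, so it is read here as MARS by elimination.

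Study design and sample specifies simple randomisation and reports 61 completers, 30 intervention and 31 control. For scores, Data Analysis gives a Mann-Whitney test, or, when normality holds, a Student's "t test was used to compare the mean scores that showed normal distribution". It mentions no covariate, change score or repeated-measures model.

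**The concern.** Every outcome score in the described schedule is taken after the app could have acted. The 1-month score follows up to a month of reminders and messages, so it is an outcome and cannot serve as a baseline.

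With about 30 patients per arm and unstratified randomisation, the arms can differ by chance in initial quality of life. A reader shown a MIDAS difference at 6 months could not check how the arms compared on MIDAS at the start, and the analyst could not adjust for it. If early MIDAS predicts later MIDAS, the unadjusted test also carries variance that a baseline covariate would have removed.

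**Working it through.** **The plan's own figure.** Inputs from Study design and sample: standardised effect 0.92, 95% power, significance level 0.05, 27 per group. An exact t-test calculation gives 27 per group one-sided (power 95.5%) and 32 per group two-sided (27 per group gives 91.3%). The stated 54 therefore reproduces as a one-sided calculation; sidedness is not stated. The figure of 33 per group follows from 27 × 1.2 = 32.4, rounded up. Neither calculation includes a baseline covariate.

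**Chance starting difference.** In SD units, for 30 and 31 patients:
- SD = √(1/30 + 1/31) = 0.256.
- 95% range = ±1.96 × 0.256 = ±0.50 SD.
- Gap of 0.3 SD or more: 0.3/0.256 = 1.17, two-sided probability 24%.
- Gap of 0.5 SD or more: 0.5/0.256 = 1.95, probability about 5%.

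A gap g carries r × g into the follow-up comparison, where r is the baseline-to-follow-up correlation. At an assumed r = 0.5, a 0.3 SD gap carries 0.15 SD and a 0.5 SD gap carries 0.25 SD.

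**Precision.** The documents give no value for r, so a range is shown. With a linear baseline covariate, residual variance is multiplied by 1 − r², the equivalent unadjusted sample is 61/(1 − r²), and the detectable difference is multiplied by √(1 − r²). The unadjusted two-sided t test at 30 and 31 detects 0.729 SD with 80% power.

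| Assumed r | 1 − r² | Equivalent patients | SE (SD units) | Detectable at 80% power | Power for 0.5 SD | Power for 0.92 SD |
|---|---|---|---|---|---|---|
| no covariate | 1.00 | 61 | 0.256 | 0.73 | 48% | 94.2% |
| 0.1 | 0.99 | 62 | 0.255 | 0.73 | 49% | 94.4% |
| 0.2 | 0.96 | 64 | 0.251 | 0.71 | 50% | 95.0% |
| 0.3 | 0.91 | 67 | 0.244 | 0.70 | 52% | 95.9% |
| 0.5 | 0.75 | 81 | 0.222 | 0.63 | 60% | 98.3% |
| 0.7 | 0.51 | 120 | 0.183 | 0.52 | 77% | 99.9% |

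The 0.5 SD effect is illustrative. The table leaves out the cost of estimating the slope: one degree of freedom, and on average about 1/(61 − 4) = 1.8% of variance. At r = 0.1 this cancels the gain (0.99 × 1.018 = 1.01). From r = 0.2 upward a gain remains (0.96 × 1.018 = 0.98).

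**The case against.** The strongest reply is that randomisation already deals with this. An unadjusted comparison of follow-up scores is unbiased on average, and its standard error already includes chance differences in starting prognosis. That stands. A reader might infer that the missing baseline makes the comparison biased or invalid; the documents do not support that. Unseen imbalance and lost precision are also two views of the same variance, and should not be counted as separate harms.

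A reader might also infer that baseline comparability cannot be examined at all. That goes too far: the form is completed for all patients before discharge, and Data Analysis has tests suited to comparing the groups on its items. Only the outcome scores are unseen.

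Next, an in-hospital score may mean little in patients with a first STEMI. For MARS this largely stands: a pre-discharge value would describe adherence to earlier medicines, if any. For MIDAS it stands in part. Data collection tool presents it as a measure for people with MI, which these patients are, but domains such as diet, concerns over medication and medication side effects concern a life with MI that has barely begun. A covariate need only predict the outcome, but the correlation could be low. The 1 − r² figures also assume a linear model, whereas the plan uses Mann-Whitney for non-normal scores.

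Power is already 94.2% at the effect used for planning. That is so if 0.92 is true for the outcome at hand, but the outcome behind it is not named.

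Finally, Figure 2 follows the schedule and is not shown. It could list a baseline scale. The text does not, and the analysis describes no use for one.

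**Conclusion.** The point holds as a limit on precision and on what can be shown. In the readable text no outcome scale precedes the intervention, so starting differences in MIDAS, and in MARS if that is what 'IUBÖ' means, can be neither displayed nor adjusted for.

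The size depends on a correlation that the documents do not give. At 0.1 to 0.2 the 61 patients would be worth about 62 to 64, and at 0.1 there is no net gain. At 0.5 they would be worth about 81. The 120 at 0.7 is the favourable end and should not be quoted alone. For an effect of 0.92, correlations of 0.3 to 0.7 add about 2 to 6 points of power; for a 0.5 SD effect they add about 4 to 28.

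This is a worthwhile, inexpensive improvement to the plan. It is not evidence that a result from this trial is wrong.

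**What to change.** **In the plan.** Have all patients complete MIDAS at the existing pre-discharge session, before the group is revealed, training is given and the app is installed. Analyse follow-up MIDAS with baseline MIDAS as a covariate, by ANCOVA at a named time point or in a repeated-measures model. Collecting the score without changing the model would recover no precision, because the stated tests would not use it. A baseline MARS is optional, for the reason given above. Define 'IUBÖ' or replace it with the name used in Data collection tool.

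The cost is one 35-item questionnaire, a few minutes per patient, and one degree of freedom; no extra visit or staff. The downside is an acute-phase score that may predict only modestly, in which case the gain is small but no bias is introduced.

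**Now.** Study design and sample reports the study as completed, so a baseline scale can no longer be added. What remains is to:
- state that no outcome baseline exists, or, if Figure 2 shows one, reconcile the text with it;
- not use the 1-month score as a baseline;
- add an analysis adjusted for a few prognostic pre-discharge form items, chosen without reference to outcome results and labelled post hoc.

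This needs no new data, only analysis time and a short limitation statement.
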